#### **4.2.3 Subject Stopping Criteria:**

Dosing will be permanently stopped for any individual subject experiencing any of the following:

- Any SAE, regardless of causality to the study drug.

- Subject experience DLT.
- Hypersensitivity or anaphylactic reaction following start of infusion.
- Medical condition that is judged by the Investigator as to jeopardize the subject's safety if he or she continues to receive the study drug.
- QTc prolongation defined as QTcF increasing  $\geq 60$  msec and persisting for at least 10 minutes or QTcF  $> 500$  msec and persisting for at least 30 minutes, or episode of torsade de pointes.

#### 4.2.4 Dose Escalation Stopping Criteria:

Dose escalation will not occur if any of the following criteria are met:

- Subject stopping rules met for  $\geq 2$  subjects in the same cohort suggesting to the Investigator that other subjects in the cohort are at risk for similar adverse drug reactions.
- Any SAE as defined in the section 10.1 in any participant receiving study drug unless obviously not related.
- $\geq 2$  out of 8 subjects experience toxicity  $\geq$  Grade 3 as defined in the Food and Drug Administration (FDA) Guidance for Industry *Toxicity Grading Scale for Healthy Adult and Adolescent Volunteers Enrolled in Preventive Vaccine Clinical Trials*.

The safety review will initially be performed on blinded data, and if any of the above criteria are met, the cohort will be subsequently unblinded to all SRC members and the safety and tolerability reassessed. Upon unblinding, the dose may be determined to be safe and tolerable, on the basis of events observed in the OsrHSA vs. placebo groups, allowing for dose escalation to proceed.

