#### **4.2.2 Dose-escalation Criteria:**

Tolerability and safety of subjects in a cohort will be reviewed by the SRC which is comprised of an independent Medical Monitor, site Principal Investigator, and Sponsor Study Director. Dose escalation may be stopped at any time based upon the Sponsor or Investigator's clinical assessment or judgment. Upon completion of the DLT observational period (first week after dosing), the SRC will examine safety data through Week 1 for each dose cohort in combination with all available, previously accumulated safety data, as well as available PK data, if any, from all subjects enrolled in the study to date. All cohorts will enroll 8 subjects (safety data from at least 6 or 7 subjects would be needed for SRC meeting, in case a subject discontinues the study), if no more than 2 out of 8 subjects experiences DLT as defined in the section 4.2.1, dose will be escalated to the next dose level.

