### **6.4.3 Subject Replacement**

Subjects who do not receive the full dose of study drug, or who withdraw from the study or with significant protocol violations may be replaced at the discretion of the investigator after informing the Sponsor.

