### **10.9 Safety Review Committee (SRC)**

To ensure the safety of study subjects and integrity of the study data, a Safety Review Committee (SRC) consisting of the study Investigators, Study Director, designated Medical Monitor and/or other key study personnel will convene to review cumulative data for the study. SRC will conduct dose decision teleconference meeting before each dose escalation.

Before each dose escalation, the Investigators, Study Director and Medical Monitor(s), together, will review the safety data from the current cohort after enough subjects (7-8) have completed the first week. It will be determined whether escalation to the next dose level can proceed or whether dose level should be de-escalated.

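### A met 4.2.4 criterion blocks escalation and triggers SRC reassessment, but nothing pauses dosing meanwhile at the current level, of replacements, or in a next cohort already under way

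*Combined protocol and SAP*

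**What the plan says.** Section 4.2.4 introduces its three criteria with "Dose escalation will not occur if any of the following criteria are met". The criteria are:

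- Criterion 1: subject stopping rules met in at least two subjects of one cohort, "suggesting to the Investigator that other subjects in the cohort are at risk for similar adverse drug reactions".
- Criterion 2: any SAE "in any participant receiving study drug unless obviously not related". It is not limited to one cohort or to the first week.
- Criterion 3: at least 2 of 8 subjects with toxicity of Grade 3 or higher.

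If any criterion is met, the SRC is unblinded to the cohort and reassesses it. Escalation may then proceed if the dose is judged tolerable.

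The one mandatory stop to dosing is in 4.2.3: "Dosing will be permanently stopped for any individual subject experiencing any of the following". Under 6.4.3, subjects who did not receive the full dose, who withdrew, or who had significant violations "may be replaced at the discretion of the investigator after informing the Sponsor". That section makes no exception while a 4.2.4 criterion stands.

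The SRC meets before each escalation, on first-week data. Section 10.9 gives it two outcomes: "It will be determined whether escalation to the next dose level can proceed or whether dose level should be de-escalated".

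**The concern.** The triggers are broader than the consequence attached to them. Criterion 1 speaks of danger to other members of the same cohort, and criterion 2 treats one possibly related SAE as serious enough to stop the dose rising. Yet the stated dosing consequence protects only people who would receive the next dose. A volunteer due to be infused at the dose that produced the event is not mentioned. Nor is a replacement subject, or a member of the next cohort when a late SAE occurs in the previous one.

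The subjects are healthy volunteers given a single infusion, and safety is the primary objective. Stopping the affected individual does nothing for the next volunteer, and little for the affected one once the infusion has ended. Whether further infusions wait for the SRC is left to someone choosing to hold them.

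**Working it through.** **1. Provisions side by side.**

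| Section | What it acts on | Set off by a met 4.2.4 criterion? |
|---|---|---|
| 4.2, 4.2.4 | Escalation to the next level (provisional) | Yes |
| 4.2.4 | SRC unblinding and reassessment of the cohort | Yes |
| 4.2.3 | Dosing of the affected individual | No; it has its own triggers |
| 4.2.2, "Dose escalation may be stopped at any time based upon the Sponsor" (or on the Investigator's judgment) | Escalation only | No; judgment |
| 5.3, exclusion 20; 6.4.1 | One subject at a time | No; judgment |
| 6.4.3 | Replacement allowed, not required | No |
| 10.8 | Termination or suspension of the study | No; judgment |
| 10.9 | De-escalation, at the pre-escalation meeting | No; judgment |

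Two responses follow automatically from a met criterion: the escalation block and the SRC reassessment. Neither is a hold on infusions.

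**2. Planned size.** Table 2 gives 5 cohorts of 8, split 6:2. So 5 × 8 = 40, which agrees with 5.1 and 11.2 (30 on OsrHSA, 10 on placebo).

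**3. Same cohort: planned subjects still undosed.** The available text gives no dosing order. Assume that *g* subjects are infused together and that the event is known before the next group starts.

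*Criterion 2*, with the one affected subject equally likely in any of 8 positions:

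- g = 1: mean (7+6+5+4+3+2+1+0)/8 = 3.5, maximum 7
- g = 2: mean (6+4+2+0)/4 = 3.0, maximum 6
- g = 4: mean (4+0)/2 = 2.0, maximum 4
- g = 8: 0

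If the affected subject was on OsrHSA, 5 of the other 7 are too. The means on OsrHSA are then 3.5 × 5/7 = 2.5, 3.0 × 5/7 = 2.1, 2.0 × 5/7 = 1.4, and 0.

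*Criterion 1*, counted at the second affected subject, with all 28 pairs of positions equally likely:

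- g = 1: the later of two positions averages 6, so 8 − 6 = 2.0, maximum 6
- g = 2: (6×1 + 4×5 + 2×9 + 0×13)/28 = 44/28 = 1.6, maximum 6
- g = 4: 4×6/28 = 0.9, maximum 4
- g = 8: 0

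These figures are conditional on a criterion having been met. The documents give no event rate, so they say nothing about how likely that is.

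**4. Next cohort.** Escalation follows first-week data (4.2.2), while AEs are followed for 30 days (7.1). Related SAEs stay reportable however long after the dose (10.4). Criterion 2 can therefore be met after the next cohort has begun. Before that cohort's first infusion the escalation block itself applies. After it, at most 8 − 1 = 7 remain undosed. The dose steps are 40/20 = 2.0, 80/40 = 2.0, 140/80 = 1.75 and 200/140 = 1.43.

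**5. Cohort 5.** No level above 200 mg/kg is planned (going higher would need an amendment under 4.2). In the last cohort the escalation block has no planned level to act on, and only the SRC reassessment remains.

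**The case against.** The best defence is that the plan already responds to a met criterion. SRC unblinding and reassessment are mandatory, SAEs reach the sponsor within 24 hours (10.4), and 10.8 lets the investigator or the sponsor end the study and contemplates suspension. A prudent investigator would hold the next infusion. All of this stands and lowers the urgency. A reader might infer that a met criterion provokes no required action, or that escalation is then barred for good. Section 4.2.4 says otherwise on both counts. What remains is that none of these provisions pauses dosing until the reassessment is done.

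Three other stronger readings also fail.

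- *That criterion 3 exposes subjects in the same way.* It is counted out of 8 and tied to the safety review, which follows the first week. It reads most naturally as an end-of-cohort test, although two early events could satisfy it sooner.
- *That up to two planned subjects are routinely still waiting at the scheduled review*, because "safety data from at least 6 or 7 subjects would be needed for SRC meeting". That allowance covers a subject who discontinues. All cohorts enrol 8, and 10.9 asks for 7 to 8 who have completed week 1.
- *That replacements would necessarily be dosed at the offending level.* Replacement is optional, and the same allowance means the SRC can meet without it.

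It can also fairly be said that the counts rest on an assumed dosing order and have a lower bound of zero. Section 2.2, Figure 1 and the Pharmacy Manual were not available to read, and any of them might state a stagger.

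**Conclusion.** The concern holds as a gap in the consequence attached to 4.2.4. In the text available, nothing automatically pauses infusions at the current level, of replacements, or in a next cohort under way while the SRC reassesses. It is clearest for criteria 2 and 1. Planned subjects exposed in the cohort range from 0 (all 8 dosed together) to at most 7 (one at a time, event in the first subject). Up to 7 could be exposed in a next cohort already started, at 1.4 to 2.0 times the dose.

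Confidence is high on the absence of a hold. It is much lower on the practical effect, which depends on an unstated dosing order and an unknown event rate. The point should be fixed because the trigger concerns people whom the consequence does not cover. The documents do not support a claim that subjects will in fact be dosed unsafely.

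**What to change.** Amend the lead-in to 4.2.4 so that, if any criterion is met, escalation does not occur **and** all further dosing is paused until the unblinded SRC reassessment that 4.2.4 already requires is complete. State that the pause covers the current cohort (cohort 5 included), replacement subjects, and any other cohort in progress. Add a line to 10.9 that this review is convened ad hoc when a criterion is met, without waiting for the next pre-escalation meeting.

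The sponsor should set the conditions for resuming. It should also decide how to limit unblinding in mid-cohort, since 4.2.4 unblinds every SRC member and 4.2.2 makes the Principal Investigator one of them.

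The cost is one clause and one line of text. In operation it is a short delay and an occasional unscheduled SRC call, only when a criterion has been met.

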In summary, OsrHSA has shown acceptable safety profile at dose level of 35.7 mg/kg. The proposed starting dose of 20 mg/kg in the current protocol is justified by 1.8-fold lower than the tested dose in China and considered to be safe.

## **5 PATIENT POPULATION**

### **5.1 Number of Subjects and Description of Population**

This study will enroll up to 40 healthy male or female subjects, 8 subjects for each of 5 cohorts, 18-55 years old, or more subjects might be recruited based on emerging data from this study and ongoing China clinical trial. Subject Selection and Numbering:

### **5.2 Inclusion Criteria**

Subjects must meet all the following criteria to be enrolled in the trial:

1. Able to understand and willing to sign the ICF
2. Healthy male and female subjects, non-smokers, 18-55 years of age, non-smokers, or subjects must have been non-smoking for at least 3 months prior to their screening visit
3. Has adequate venous access
4. With no significant medical history, and in good health as determined by detailed medical history (neurological, endocrinal, cardiovascular, pulmonary, hematological, immunologic, psychiatric, gastrointestinal, renal, hepatic, and metabolic disease), full physical examination,

vital signs, 12-lead electrocardiogram (ECG), urinalysis and laboratory tests at screening. For eligibility purposes, abnormal laboratory or vital signs results may be repeated once if abnormal result is observed at the initial reading. Moreover, abnormalities found in the ECG may need to be confirmed by repeated measurements.

5. Subjects must have adequate organ function according to the following laboratory values:
  - Bone marrow function (absolute neutrophil count  $\geq 1500/\text{mm}^3$  and platelet count  $\geq 100,000/\text{mm}^3$ )
  - Adequate liver function [alanine aminotransferase (ALT)  $\leq 1.5 \times$  upper limit normal (ULN) and alkaline phosphatase  $\leq 1.5 \times$  ULN, total bilirubin  $\leq 1.5$  mg/dL]
  - Adequate renal function creatinine clearance  $\geq 60$  mL/min based on Cockcroft- Gault equation, or serum creatinine level  $\leq 1.5$  times the ULN.
6. Be a female of non-childbearing potential (i.e., physiologically incapable of becoming pregnant, including any female who is 2 years post-menopausal and have an FSH  $> 40\text{mIU/mL}$ , or surgically sterile [defined as having a bilateral oophorectomy, hysterectomy or tubal ligation]) or agree to one of the following to prevent pregnancy and, if a woman of childbearing potential, have a negative urine pregnancy test at screening:
  - Practicing abstinence
  - If a sexually active woman of childbearing potential (sexually active with a non-sterile male partner) agrees to prevent pregnancy by using double methods of contraception as follow until at least 30 days after the administration of the investigational product:
    - a. simultaneous use of intra-uterine contraceptive device, placed at least 4 weeks prior to study drug administration, and condom for the male partner;
    - b. simultaneous use of hormonal contraceptives, starting at least 4 weeks prior to study drug administration and must agree to use the same hormonal contraceptive throughout the study, and condom for the male partner;
    - c. simultaneous use of diaphragm with intravaginally applied spermicide and male condom for the male partner, starting at least 21 days prior to study drug administration.
  - Male subjects who are not vasectomized for at least 6 months and who are sexually active with a non-sterile female partner must agree to use double methods of contraception below

from the first dose of randomized study drug until 90 days after their dose and must not donate sperm during their study participation period:

- a) simultaneous use of a male condom and, for the female partner, hormonal contraceptives (used since at least 4 weeks) or intra-uterine contraceptive device (placed since at least 4 weeks);
  - b) simultaneous use of a male condom and, for the female partner, a diaphragm with intravaginally applied spermicide.
7. Body mass index (BMI) 18-30 kg/m^2 and body weight  $\geq$  50.0 kg for males and  $\geq$  45.0 kg for females.
  8. Blood pressure  $\leq$  139/89 mm Hg.
  9. Subjects are able to follow the study protocol and complete the trial.
  10. At least 25% of the enrolled subjects will be of Asian descent, defined as Chinese, Japanese, Korean, Vietnamese, Hmong, and their offspring.

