Study Design:	
This is a Phase 1 randomized, double blinded, placebo-controlled, single dose escalation study to evaluate safety, tolerability, PK, and immunogenicity of OsrHSA in healthy volunteers (See study design schema).
 
After a screening period of up to 28 days, the qualified subjects will be randomized to OsrHSA or placebo (6:2). Each enrolled subject will receive one single assigned dose of OsrHSA or placebo. The investigator and subjects will be blinded to treatment assignment. During the study, subjects will be evaluated for safety and tolerability, PK/PD, and activity of OsrHSA.
 
On day 1, OsrHSA or placebo will be administered as single IV infusion at a rate lower than 2 ml/min to the subjects. Patients will be observed overnight. On Day 2, after completion of the study procedures and assessments, subjects will be discharged from the clinical research center. Seven-day dose-limiting toxicity (DLT) observational period will commence upon completion of dosing at the end of infusion (EOI). Subjects will have end-of-study (EOS) follow-up visits on Day 30 after infusion.
 
The planned doses are 20, 40, 80, 140, and 200 mg/kg, dose level(s) higher than 200mg/kg might be an option(s) based on emerging data from this study and ongoing China clinical trial (China IND#: CXSL1500135; Protocol Number: HY1001) .

Dose escalation decisions will be determined based on toxicities data as well as available all available PK data observed within 7 days after dosing.

**Study participation  
Duration:**

The screening period is up to 28 days, one treatment day, and follow-up period of 30 days

**Pharmacokinetic (PK)  
evaluations:**

Blood samples for single dose PK will be collected from all subjects to determine the albumin concentration changes, they will be taken at time points listed in [Table 1](#). The PK of OsrHSA will be analyzed using standard non-compartmental analysis (NCA) by validated software WinNonLin version 6.4 or higher (Certara, NJ, USA). PK parameters derived from NCA analysis will include, but not limit to,  $AUC_{0-\infty}$  and  $AUC_{0-t}$ ,  $C_{max}$ ,  $t_{1/2}$ , CL, and  $V_d$ . PK parameters will be listed for each subject and summarized with descriptive statistics by each dose level/cohort. PK parameters will also be presented with baseline corrected.

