13. PK samples (Serum albumin) will be collected at pre-dose, 0.5h after dose initiating, EOI, and 0.5h, 4h, 12h, 24h (Day 2), 48h (Day 3), Day 5, Day 8, Day 15, Day 22, and Day 30 post EOI. The exact/actual time to collect blood will be documented.
14. Colloid osmotic pressure will be measured within 30 min predose, every 30 min after dose initiating until EOI, EOI, every 1 hour up to 6 hours post EOI, every 2 hour after 6 hours up to 12 hours post EOI, and every 4 hours until 24 hours post EOI or discharge, 48h (D3), D5, D8, D15, D22, and D30 post EOI. Blood pressure should be measured prior to each colloid osmotic pressure sampling.
15. Blood samples for ADA and Anti-HCP antibody analyses will be collected at pre-dose, D8, D15, D22, and D30 post EOI.

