### 4.2 Study Process

The trial will include a screening period, treatment period, and follow-up period of 30 days after administration. The screening period will be up to 28 days prior to investigational product administration. The screening process will initiate upon completion of the informed consent process. Once consent is provided by each participant, a thorough screening process will take place, including detailed medical history, physical examination, vital signs, concomitant medications, safety labs (see Table 1), 12 lead electrocardiogram, urine pregnancy test, urinalysis, serology panel (refer Table 1), assessment of inclusion and exclusion criteria. Upon completion of the screening, qualified subjects will be randomized to OsrHSA or placebo (6:2). Each enrolled subject will receive one single assigned dose of OsrHSA or placebo. The investigator and subjects will be blinded to treatment assignment. During the study, subjects will be evaluated for safety and toxicity, PK/PD, and activity of OsrHSA.

OsrHSA or placebo will be administered as single IV infusion at a rate lower than 2 ml/ min to the subjects. The actual start and stop times of the infusions, along with any interruptions in the infusion will be recorded. Subjects will have end-of-study (EOS) follow-up visits on Day 30 after infusion.

The planned doses are 20, 40, 80, 140, and 200 mg/kg (Table 2), dose level(s) higher than 200 mg/kg might be an option(s) based on emerging data from this study and ongoing China clinical trial, if that is the case, an amendment will be submitted.

The protocol for the repeat dose study will be submitted as an amendment to the IND after the single dose study has been completed and analyzed. The dose schedule of the repeat dose study will be based on results obtained from the single dose study. The safety of the dose that will be used in the repeat dose study will be established before the initiation of the repeat dose study.

Dose escalation will occur sequentially after review of safety data for each dosing cohort by the safety review committee (SRC). Dose escalation to the next dose level will proceed uninterrupted as long as no pre-defined DLT or stopping criteria are met.

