### **5.7 Activity**

Subjects should refrain from strenuous exercise for 48 hours before admission to the clinical center and throughout the study. Subjects may participate in light recreational activities during the study (eg, watching television, reading).

Subjects will be advised not to donate blood or plasma from at least 12 weeks before study drug administration and for at least 3 months after the last dose administration.

For safety reasons, subjects will be required to remain semi-reclined and avoid lying down or sleeping for the first 4 hours after the end of study drug infusion. However, failure of subjects to comply with these requirements does not constitute a deviation from the protocol if it is medically necessary, procedurally required, or to go to the bathroom. When appropriate, subjects will be accompanied by a staff member during ambulation.

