## **6.4 Removal from Study Treatment and off-Study Criteria**

Participation in this research study is completely voluntary. Subjects are free to withdraw from this study at any time by informing the investigator. If a subject, for whatever reason, no longer appropriate to continue receiving study therapy, they will be notified and withdrawn from the study. Furthermore, if the subject is non-compliant (e.g. non-compliant with visits, concomitant medications.) they will be withdrawn from the study and a replacement subject may be recruited.

Additionally, prior to removal from study, effort must be made to have all subjects complete a safety visit approximately 30 days following the last dose of study therapy.

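### Covered men must use double contraception until 90 days after the dose, but the sperm-donation bar normally lapses at the Day 30 visit, about 60 days earlier

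*Combined protocol and SAP*

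**What the plan says.** Section 5.2, item 6, is addressed to "Male subjects who are not vasectomized for at least 6 months and who are sexually active with a non-sterile female partner". These men must use two methods of contraception "from the first dose of randomized study drug until 90 days after their dose and must not donate sperm during their study participation period". The item does not define the participation period.

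Three other places bear on its length:

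- The synopsis row on the duration of participation reads "The screening period is up to 28 days, one treatment day, and follow-up period of 30 days".
- Section 4.2 states "The trial will include a screening period, treatment period, and follow-up period of 30 days after administration" and "Subjects will have end-of-study (EOS) follow-up visits on Day 30 after infusion".
- Table 1 puts the last visit at D30, with a window of 2 days either side.

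Section 7.1 lets adverse-event follow-up run past 30 days if a drug-related toxicity has not resolved. The only other donation restriction in the available text is in section 5.7. It concerns blood and plasma, and advises against donation before dosing "and for at least 3 months after the last dose administration". It does not mention sperm.

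**The concern.** One sentence gives the same men two reproductive precautions with different end dates, and the plan gives no reason for the difference. Donation is another route to conception. If the sponsor wants a treated man to prevent conception for 90 days, a donation bar that lapses at about Day 30 does not serve that purpose for the remaining time. A man who follows the criterion to the letter is then under no stated bar in the available protocol text, although he must still use two contraceptive methods with his partner.

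What is at stake is a small gain in reproductive safety and a consistent instruction to participants. No statistical quantity depends on it.

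**Working it through.** The plan states no figure for this gap, so there is none to reproduce. The check is date arithmetic.

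**Inputs**

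- End of required male contraception: 90 days after the single dose (section 5.2, item 6; section 6.3).
- End of participation: the Day 30 visit, within 2 days either side (synopsis, section 4.2, Table 1).
- Day count: section 4.2 counts Day 30 from the infusion. Table 1, footnote 13, labels post-infusion samples "24h (Day 2), 48h (Day 3", and so on, which would put Day 30 at 29 days.

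**Formula**

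Gap = (days from dose to end of contraception) − (days from dose to last visit).

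| Day count | Nominal | Late visit (+2 d) | Early visit (−2 d) |
|---|---|---|---|
| Day 30 = 30 days after infusion | 90 − 30 = 60 | 90 − 32 = 58 | 90 − 28 = 62 |
| Day 30 = 29 days after infusion | 90 − 29 = 61 | 90 − 31 = 59 | 90 − 27 = 63 |

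The overall range is 58 to 63 days, so about 60 days on either count.

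**Departures from the usual course**

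- If follow-up is extended for an unresolved drug-related toxicity, and that time counts as participation, the gap is shorter for that man.
- For early withdrawal, section 6.4 says "effort must be made to have all subjects complete a safety visit approximately 30 days following the last dose of study therapy". If he attends, and the contraception commitment still holds, the gap is again about 90 − 30 = 60 days.

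**Check of the fix**

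With the bar extended to 90 days after the dose, the gap is 90 − 90 = 0.

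**Number of men**

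Table 2 gives 5 × 6 = 30 subjects on OsrHSA and 5 × 2 = 10 on placebo, both sexes together. The plan does not fix the sex split, so the number of men affected cannot be derived.

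**The case against.** The strongest reply is that no consequence is shown. Section 2.3.3 reports no toxicity specific to OsrHSA and negative genotoxicity tests. The available text states no reproductive hazard and no reason for 90 days. The same item asks women of childbearing potential for contraception until at least 30 days after dosing. The 90 days may therefore be the cautious outlier, and shortening male contraception would remove the mismatch just as well. After Day 30 no scheduled visit checks either commitment. All of this stands, and it is why the point is minor. It does not explain why one sentence sets two end dates.

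The blood-donation advice in section 5.7 shows that the authors could write a period outlasting the last visit. It has no stated reproductive rationale, so it does not show that the shorter sperm bar was a slip.

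Several stronger readings are tempting and are not supported:

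- *Men are left uninstructed, or are permitted to donate.* The protocol is silent after participation, which is not permission. The consent pages, and some protocol text around sections 2.2 and 4.3, are not in the copy reviewed. A longer bar or a rationale could be there.
- *The gap reaches 90 − 1 = 89 days for a man who leaves at 24 hours.* This assumes that a withdrawn man who skips the safety visit remains bound by the contraception agreement. The documents do not say so.
- *Placebo men learn their allocation at Day 30, so the gap matters only for treated men.* Section 5.8 ties unblinding to the completion of participation but does not clearly say that it happens man by man at that visit.
- *Section 2.3.2 settles the hazard by likening OsrHSA to endogenous albumin.* That sentence concerns drug transport and CYP interactions. The low-hazard judgement rests on section 2.3.3 instead.

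The opposite reading, that participation itself runs 90 days, also fails. The synopsis gives 30 days of follow-up, and item 6 uses a different phrase for donation from the one it uses for contraception.

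**Conclusion.** The mismatch is real and small. For about 60 days per completing covered man (58 to 63), the available protocol text does not bar sperm donation while contraception is still required. This assumes that participation ends at the Day 30 visit, which the synopsis, section 4.2 and Table 1 support. It also assumes that no text outside the copy reviewed extends the bar.

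The hazard is probably low, and no endpoint, escalation rule or analysis changes.

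The narrow coverage of the bar is a separate and secondary matter. Donation does not depend on having a fertile partner, yet only men with one are covered. A reader might take this as a second defect of equal weight. The documents show no hazard that would justify that, so it is offered only as an optional improvement.

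**What to change.** In item 6, change the donation clause to: *must not donate sperm during study participation and until 90 days after their dose*. Keeping the reference to participation preserves any cover before dosing, and the added end date closes the gap. Match the consent text if it differs.

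Optionally, make this a separate line for all men not vasectomized for at least 6 months, whatever their partner status.

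The cost is a minor amendment, which section 8.2 makes subject to sponsor agreement and ethics approval. Covered men would have about 60 more days of donation restriction, ending at 90 rather than about 30 days after the dose. Under the optional line, newly covered men would be restricted for up to about 28 + 90 = 118 days if participation counts from screening. No visit, procedure or analysis changes. Shortening male contraception would also align the two dates, but it is the less cautious choice. If the sponsor prefers to keep different dates, the reason should be stated.
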